9.2 SAMPLE SIZE DETERMINATION

Based on the primary variable of the intervention, the percentage of T2DM remission, the required sample size has been calculated to observe statistically significant differences. This variable will be coded dichotomously. A total of 120 volunteers (60 per arm) will be recruited for the study. Accepting an alpha risk of 0.05 (5%) and a beta risk of less than 0.2 in a two-sided test, at least 52 subjects in the control group and 52 subjects in the intervention group would be required to detect as statistically significant a 20% difference between two proportions (primary endpoint: T2DM remission). For the control group, the expected remission rate ranges from 0 to 5%, whereas in the intervention group, it is expected to be at least 25%. The remission rates have been benchmarked against previous studies (Lean et al., n.d.). An estimated loss to follow-up rate of 15% has been considered.

Given the estimated 15% loss to follow-up, the sample size has been increased to 60 participants instead of 52. This ensures that the statistical power of the analysis will be preserved.

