9.4 STATISTICAL ANALYSES

9.4.1 GENERAL APPROACH

The statistical analysis will consist of two sub-analyses. First, a descriptive analysis will be performed, followed by an analysis to determine differences between the intervention and control groups. These analyses will be conducted using STATA/MP statistical software.

In the initial descriptive analysis, qualitative variables (e.g., sex, socioeconomic status) will be described using absolute and relative frequencies. Continuous variables (e.g., age, HbA1c, weight, BMI, blood pressure, cholesterol, HOMA-IR) will be described using mean and standard deviation for normally distributed variables, or median and interquartile range for variables with non-normal distributions. Normality of quantitative variables will first be assessed using the Kolmogorov-Smirnov test. Group comparability will be assessed using standardized mean differences (SMD), with $SMD < 0.10$ indicating negligible imbalance and $SMD \geq 0.20$ indicating meaningful imbalance. Formal hypothesis testing at baseline will not be routinely performed; if included, such p-values will be reported as descriptive only.

The primary efficacy analysis will use analysis of covariance (ANCOVA), with the 6-month value of the primary outcome as the dependent variable and the baseline value as a covariate. The model will include prespecified covariates: baseline outcome, age, sex, site (if applicable), and block/stratum used in randomization. The primary result will be the adjusted mean difference between intervention and control. Absolute risk reduction, relative risk reduction, and number needed to treat will also be calculated.

The secondary efficacy analysis will be a longitudinal analysis. The effect of the intervention in terms of T2DM reversal or remission (dichotomous variable) will be estimated using a mixed-effects model for repeated measures (MMRM) with a random intercept for participant and fixed effects for time, group, and group \times time interaction.

All statistical tests will be two-sided, with a significance level of $\alpha = 0.05$ considered statistically significant.

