9.4.2 ANALYSIS OF THE PRIMARY ENDPOINT(S)

The primary endpoint is the change in glycated hemoglobin (HbA1c, %) from baseline to 6 months. HbA1c is measured as a continuous variable on an interval scale. The endpoint will be calculated as the absolute difference between baseline HbA1c and the value obtained at 6 months.

The primary analysis will be performed using analysis of covariance (ANCOVA) with treatment group (intervention vs. control) as the fixed factor, and baseline HbA1c as a covariate to improve precision. Additional prespecified covariates will include age, sex, study site, and randomization block, based on their potential clinical relevance and to ensure adjustment for any residual imbalance despite randomization. A secondary, confirmatory analysis will be conducted using a

mixed-effects model for repeated measures (MMRM), which includes all available timepoints (baseline, 3 months, and 6 months). This model accounts for within-subject correlation by specifying an unstructured covariance matrix.

Results will be presented as adjusted mean differences between groups with 95% confidence intervals and corresponding two-sided p-values. Least-squares means (LSMEANS) will be used to report group means adjusted for covariates.

The Intention-to-Treat (ITT) population will be the primary analytic set, including all randomized participants according to their allocated group. A Per-Protocol (PP) population, defined as participants with at least 70% adherence to the intervention, will be analyzed as a sensitivity approach.

Handling of Missing Data; for ANCOVA, missing data at 6 months will be addressed using multiple imputation under the missing-at-random (MAR) assumption. In MMRM, missing data are implicitly handled under MAR. Additional sensitivity analyses will explore the robustness of results to different missing-data mechanisms.

For ANCOVA, residuals will be checked for normality and homoscedasticity. If these assumptions are substantially violated, transformations or nonparametric methods will be considered. For MMRM, model fit will be evaluated and alternative covariance structures tested.

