9.4.3 ANALYSIS OF THE SECONDARY ENDPOINT(S)

The secondary endpoint is diabetes remission at 18 months, defined as achieving HbA1c <6.5% without glucose-lowering medications. It will be analyzed using a generalized linear mixed-effects model (GLMM) with a logit link, including treatment group, time, and group \times time interaction as fixed effects, and a random intercept for participants to account for repeated measurements. Prespecified covariates include baseline HbA1c, age, sex, site, and randomization block. Results will be reported as adjusted odds ratios with 95% confidence intervals and two-sided p-values.

The analysis will follow the Intention-to-Treat (ITT) principle; a Per-Protocol (PP) analysis (adherence $\geq 70\%$) will be performed as sensitivity. Missing data will be handled under the missing-at-random assumption, with multiple imputation applied if necessary. Trajectories of remission probabilities over time will also be presented.

Others secondary endpoints include:

- Change in body weight (kg) from baseline to 6 months (continuous, interval scale).
- Change in blood pressure (systolic and diastolic, mmHg) from baseline to 6 months (continuous, interval scale).
- Change in lipid profile (total cholesterol, LDL-C, HDL-C, triglycerides, mg/dL) from baseline to 6 months (continuous, interval scale).
- Change in circadian rhythm regularity (measured via validated questionnaire scores; ordinal/interval scale).

- Change in health-related quality of life (measured via validated scale, e.g., SF-12 or equivalent; interval scale).
- Intervention adherence (measured as percentage of scheduled sessions completed; continuous, but categorized as adherent $\geq 70\%$ vs. non-adherent for analysis).

The analysis models for continuous outcomes (e.g., weight, blood pressure, lipid levels, quality of life scores) will be analyzed using ANCOVA with treatment group as a fixed factor and baseline values as covariates. Repeated measures across timepoints (baseline, 3 months, 6 months) will be analyzed with MMRM to account for within-participant correlations.

For binary/categorical outcomes (e.g., adherence $\geq 70\%$, achievement of HbA1c $< 6.5\%$) will be analyzed using logistic regression, adjusted for prespecified covariates.

For ordinal outcomes (e.g., circadian rhythm scores if treated as ordinal), ordinal logistic regression will be considered.

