All analyses will adjust for baseline values of each outcome, plus prespecified covariates such as age, sex, and site. Covariate selection will be guided by clinical relevance and baseline comparability, aiming for a parsimonious model.

Results will be reported as adjusted mean changes with standard errors (for continuous outcomes), odds ratios with 95% confidence intervals (for binary/ordinal outcomes), and associated p-values. For binary endpoints, absolute risk differences and numbers-needed-to-treat (NNT) will also be reported when applicable.

The same approach as for the primary endpoint will be applied: MMRM for repeated measures (implicitly handling missing values under MAR) and multiple imputation for single-timepoint ANCOVA analyses. Sensitivity analyses will evaluate the robustness of results.

Normality and homoscedasticity will be checked for continuous outcomes. Logistic regression models will be checked for linearity in the logit and absence of multicollinearity. Ordinal models will be checked for proportional odds assumption.

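### In the repeated-measures models for the secondary continuous outcomes, baseline is both a response and a covariate, so the model cannot be validly fitted as written

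*Protocol*

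**What the plan says.** Section 9.4.3, on the secondary continuous outcomes: "Repeated measures across timepoints (baseline, 3 months, 6 months) will be analyzed with MMRM to account for within-participant correlations". Baseline is therefore one of the response rows. Later in the same section: "All analyses will adjust for baseline values of each outcome, plus prespecified covariates such as age, sex, and site". Baseline stands there beside ordinary covariates, and the sentence exempts no model. The section then says that the approach of the primary endpoint, MMRM included, is reused.

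Section 9.4.2 describes the HbA1c MMRM as a model "which includes all available timepoints (baseline, 3 months, and 6 months). This model accounts for within-subject correlation by specifying an unstructured covariance matrix". It adds: "For MMRM, model fit will be evaluated and alternative covariance structures tested". No alternative structure is named. Baseline HbA1c is named as a covariate in the ANCOVA sentence; the MMRM sentence lists no covariates.

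On the test level, section 9.4.1 says "All statistical tests will be two-sided, with a significance level of" 0.05. For HbA1c, section 9.4.2 reports adjusted between-group mean differences with least-squares means. For the secondary continuous outcomes, section 9.4.3 reports covariate-adjusted mean changes.

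**The concern.** A repeated-measures model can use baseline as a response or as a covariate. If it does both, a baseline slope of 1 predicts the baseline row exactly. With a free variance for that row, as under an unstructured covariance, the residual variance can shrink to zero and the likelihood grows without limit. The software then fails or stops at an arbitrary point.

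The analyst must then choose a repair with the data in hand. One route that the protocol leaves open is a simpler covariance. If that structure assumes one variance for all rows, the artificially small baseline residuals are pooled with the follow-up residuals, and the standard error of the 6-month difference is too small. The planned longitudinal analysis of weight, blood pressure, lipids and quality of life is at stake. This holds for any visit schedule that includes baseline.

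**Working it through.** **Inputs from the protocol.** Two-sided alpha 0.05 (9.2, 9.4.1); 60 per arm and 15% loss (9.2), so 60 × 0.85 = 51 per arm; response times and baseline adjustment (9.4.3); unstructured covariance with unnamed alternatives (9.4.2). Section 8.1 schedules laboratory tests at baseline, 6 months and 18 months, so lipids and HbA1c have two rows up to 6 months.

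**Assumed.** The within-person correlation r is not given; 0.3-0.8 is used. Variance is 1 at each visit, with one common baseline slope.

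**1. The plan's own level.** Simulated null trials (2,000 per setting, 51 per arm, REML, compound symmetry) with baseline used once reject at 6 months in 4.1-5.3% (response only) or 4.7-5.9% (covariate only). The stated 5% is reproduced.

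**2. Unstructured fit, baseline in both roles.** One simulated data set, three rows, r = 0.5; the baseline-row residual variance v is moved towards zero:

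| v | ML log-likelihood | REML log-likelihood | baseline slope |
|---|---|---|---|
| 1 | -78.7 | -93.4 | 0.710 |
| 0.01 | 146.0 | 124.7 | 0.994 |
| 0.0001 | 380.6 | 352.4 | 0.99994 |
| 1e-8 | 850.3 | 808.3 | 1.000 |

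There is no maximum. With baseline as response only, the ML value falls over the same steps, from -139.2 at v = 1 to -5456.9 at v = 0.01 and further below that.

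**3. Homogeneous-variance fallback, 6-month difference.** With T rows under compound symmetry, the covariate is constant within a person, so its slope is fitted from the person mean:

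- slope b = (1 + (T-1)r)/T
- baseline-row residual variance v0 = (1-b)²
- follow-up residual variance v1 = 1 - 2br + b², which is also the true per-person variance behind the 6-month difference
- variance used by the model m = (v0 + (T-1)v1)/T
- type I error = 2(1 - Φ(1.96/√(v1/m)))

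Example, T = 2, r = 0.5: b = 0.75; v0 = 0.0625; v1 = 1 - 0.75 + 0.5625 = 0.8125; m = (0.0625 + 0.8125)/2 = 0.4375; v1/m = 1.857; 1.96/1.363 = 1.438; type I error 15.0%.

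| Rows | r | b | v0 | v1 | m | v1/m | Type I error |
|---|---|---|---|---|---|---|---|
| 2 | 0.3 | 0.65 | 0.1225 | 1.0325 | 0.5775 | 1.788 | 14.3% |
| 2 | 0.5 | 0.75 | 0.0625 | 0.8125 | 0.4375 | 1.857 | 15.0% |
| 2 | 0.7 | 0.85 | 0.0225 | 0.5325 | 0.2775 | 1.919 | 15.7% |
| 2 | 0.8 | 0.90 | 0.0100 | 0.3700 | 0.1900 | 1.947 | 16.0% |
| 3 | 0.3 | 0.533 | 0.2178 | 0.9644 | 0.7156 | 1.348 | 9.1% |
| 3 | 0.5 | 0.667 | 0.1111 | 0.7778 | 0.5556 | 1.400 | 9.8% |
| 3 | 0.7 | 0.80 | 0.0400 | 0.5200 | 0.3600 | 1.444 | 10.3% |

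Simulation (compound-symmetry, random-intercept and AR(1) fits) gave 13.5-16.2% with two rows. With three rows it gave 7.7-13.6%, the highest values arising when the true correlation was AR(1). With a follow-up SD 0.8 or 1.2 times baseline and r = 0.5, it gave 8.2-14.1%.

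**4. Same fallback, difference in change.** The baseline slope cancels from 6 months minus baseline. True and model variance per person are both 2(1-r), the ratio is 1, and the level is 5%. Simulation gave 4.1-7.7% under compound-symmetry truth and 6.3-9.1% under AR(1) truth.

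**The case against.** The strongest reply is that no single sentence specifies this model. Both sections pair the baseline covariate with ANCOVA and the list of times with MMRM. The adjust-for-baseline sentence cannot be wholly literal, since intervention adherence is among the secondary outcomes and has no baseline value. A statistician would notice a diverging fit, model fit is to be evaluated, and a separate analysis plan may list the fixed effects. Part of this stands: the error is one of wording and is easily repaired. But the sentence covers all analyses, weight, blood pressure, lipids and quality of life do have baseline values, and nothing removes baseline from either role. This is a stated rule that fails, not a detail left for later.

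Four stronger readings are tempting and are not supported:

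- **That these analyses will run at 9-16% instead of 5%.** This needs a homogeneous-variance fallback, which the protocol never names, and the adjusted 6-month contrast. The random intercept in section 9.4.1 belongs to the remission model. For the secondary outcomes, section 9.4.3 reports adjusted mean changes, which is closer to the difference in change, and that stays near nominal.
- **That the HbA1c MMRM is explicitly misspecified.** The adjustment sentence sits in the secondary-endpoint section, and the reuse statement carries 9.4.2 into 9.4.3, not the reverse.
- **That the double role costs power through a change-score analysis.** With complete data and free group-by-time means, the change contrast is the difference in change scores even when baseline is a response only. The loss cannot be charged to the double role.
- **That the primary ANCOVA or the remission GLMM is affected.** The ANCOVA uses baseline only as a covariate, and the GLMM text does not make baseline a response.

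**Conclusion.** Wrong as written for the secondary continuous outcomes: followed literally, sections 9.4.2 and 9.4.3 define an MMRM whose unstructured likelihood is unbounded. That conclusion does not depend on the assumed correlation. It does rest on reading the reuse of the primary approach as carrying over the unstructured covariance. For the HbA1c MMRM the conflict is implied, not stated.

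The inflation is conditional on the fallback and the contrast. It is about 14-16% (two rows) or 9-10% (three rows) for the adjusted 6-month difference under compound symmetry with equal variances, and about 4-9% for the difference in change. The two-row figures are the relevant ones for lipids, and for HbA1c if the double role is applied there.

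**What to change.** In sections 9.4.2 and 9.4.3, give baseline one role in each MMRM. Either:

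- use post-baseline visits only as responses, with baseline and baseline-by-time as covariates; or
- keep baseline as a response with a mean common to both arms, and drop the baseline covariate from that model.

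Apply one option to all continuous endpoints. Limit the adjust-for-baseline sentence in 9.4.3 to models in which baseline is not a response. Name the visit-specific group contrast to be reported, and the fallback covariance structure. The cost is a few sentences; no new data, visits or participants are needed.

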4 STUDY DESIGN

4.1 OVERALL DESIGN

The study is designed as an open-label, randomized clinical trial. The strategy includes Group A – Intervention, which will undergo the CREDOenAP program, and a parallel control group, Group B – Control, which will receive standard T2DM care from a primary care team (family physicians

and nurses) without any intervention from the research team, except for data collection at baseline and at the end of each study phase.

The study has been designed to evaluate the effectiveness of a lifestyle-focused intervention (CREDOenAP) on T2DM reversal in primary care patients. It is a multicenter study involving two primary care centers in Barcelona (CAP Larrad and CAP Barceloneta).

The main hypothesis is that the proposed intervention, based on a structured and culturally adapted program, is effective in achieving biochemical and functional remission of T2DM. The study design corresponds to a randomized clinical trial aimed at establishing the initial efficacy of the intervention under real-world clinical practice conditions.

Each center will recruit participants who will be randomly assigned in a 1:1 ratio to each study arm. Recruitment is planned as follows:

- Center 1 (CAP Barceloneta): Group A – Intervention (20 participants) and Group B – Control (20 participants).
- Center 2 (CAP Larrad): Group A – Intervention (40 participants) and Group B – Control (40 participants).

Group A – Intervention, comprising a total of 60 participants (20 from Center 1 and 40 from Center 2), will receive standard care plus the CREDOenAP intervention.

Group B – Control, comprising a total of 60 participants (20 from Center 1 and 40 from Center 2), will receive standard care alone.

Both Group A – Intervention and Group B – Control will include patients meeting the inclusion and exclusion criteria, with assignment conducted via stratified randomization. Potential participants will be validated by a healthcare professional not involved in the intervention to exclude false positives due to registration errors.

For stratification, performed through statistical programming, relevant characteristics that may act as potential confounding variables will be considered. In this study, stratification will be based on:

- Healthcare center (Center 1: CAP Barceloneta / Center 2: CAP Larrad)
- Sex (Male / Female)
- Age (18–50 years / \geq 50 years)
- Years since T2DM diagnosis (<5 years / \geq 5 years)

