9.4.5 BASELINE DESCRIPTIVE STATISTICS

Baseline descriptive analysis of the study population will include the following: qualitative variables (sex, socioeconomic status, etc.) will be described using absolute and relative frequencies. Continuous variables (age, HbA1c, weight, BMI, blood pressure, cholesterol, HOMA-IR, etc.) will be described as mean and standard deviation for normally distributed data, or as median and interquartile range for non-normally distributed data. Normality of quantitative variables will be assessed using the Kolmogorov-Smirnov test.

Group comparability will be assessed using standardized mean differences (SMD), with $SMD < 0.10$ indicating negligible imbalance and $SMD \geq 0.20$ indicating meaningful imbalance. Formal hypothesis testing at baseline will not be routinely performed; if included, such p-values will be reported as descriptive only.

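### For the other secondary endpoints, Section 9.4.3 calls the covariates prespecified but lets observed baseline comparability guide their selection

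*Protocol*

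**What the plan says.** Section 9.4.3 lists the other secondary endpoints (weight, blood pressure, lipids, circadian regularity, quality of life, adherence) and then gives two consecutive sentences on adjustment. The first: "All analyses will adjust for baseline values of each outcome, plus prespecified covariates such as age, sex, and site". The second: "Covariate selection will be guided by clinical relevance and baseline comparability, aiming for a parsimonious model".

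The protocol measures comparability in one way only. Section 9.4.1 states "Group comparability will be assessed using standardized mean differences (SMD), with" two cut-offs, and Section 9.4.5 gives the same ones: "with $SMD < 0.10$ indicating negligible imbalance and $SMD \geq 0.20$ indicating meaningful imbalance". Neither section says that a flagged variable enters a model.

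Two analyses have their own lists. For the primary ANCOVA, Section 9.4.2 says "Additional prespecified covariates will include age, sex, study site, and randomization block", in addition to baseline HbA1c. For remission at 18 months, Section 9.4.3 says "Prespecified covariates include baseline HbA1c, age, sex, site, and randomization block".

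Section 4.1 stratifies the randomisation by centre, sex, age group and "Years since T2DM diagnosis" (cut at 5 years). Section 9.2 gives the size: "A total of 120 volunteers (60 per arm) will be recruited for the study".

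**The concern.** A covariate list is prespecified if it is fixed without reference to the randomised data. Comparability of the arms can only be judged once allocation and baseline data are in. The second sentence therefore takes back part of what the first one promises, and the words *such as* leave the list open in any case.

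Three things are at stake for the endpoints that this wording governs.

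- **Calibration.** If a prognostic covariate is adjusted for only when it happens to be imbalanced, the test no longer runs at the nominal two-sided 5%.
- **Precision.** When that covariate happens to be balanced it is left out, and the precision it would have given is lost.
- **Discretion.** The trial is open-label and the wording sets no entry rule, so a model could be settled after data have been seen by arm.

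Separately, diabetes duration was thought important enough to stratify on, yet it is not among the covariates named for these endpoints. Nor is the randomisation block or stratum, which would carry it.

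**Working it through.** The protocol gives no figure of its own on this point. The inputs taken from it are 60 per arm, 52 evaluable per arm and 15% loss (Section 9.2; 60 × 0.85 = 51), and the SMD cut-offs (Sections 9.4.1 and 9.4.5).

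**Step 1. How often chance triggers the 0.20 flag.** Under randomisation, for a continuous variable that is not stratified on, SE(SMD) ≈ √(2/n) and P(|SMD| ≥ 0.20) = 2[1 − Φ(0.20/SE)].

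- n = 60: SE = √(2/60) = 0.183; 0.20/0.183 = 1.095; P = 27.3% (27.6% with the t distribution).
- n = 52: P = 30.8%. n = 51: P = 31.3%.

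The rate is lower for variables tied to the stratification. Permuted blocks within the 16 strata were simulated, with block sizes 4 and 6 and the covariate distributions assumed. The flag rate was below 1% for sex and for site, about 9–15% for age group and about 21–24% for continuous age.

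**Step 2. What an imbalance-triggered rule would do.** ANCOVA was simulated with 60 per arm and 40,000 trials per setting. The baseline outcome is in every model, as Section 9.4.3 requires. One extra covariate enters only if |SMD| ≥ 0.20. Its partial correlation ρ with the outcome is not in the protocol, so it was varied. The effect was set to give about 80% power without the covariate: (1.96 + 0.84) × √(2/60) ≈ 0.51 residual SD.

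| ρ (assumed) | Type I error, triggered | Type I error, always in | Power, triggered | Power, always in | Power, never in |
|---|---|---|---|---|---|
| 0.1 | 5.1% | 5.1% | 79.1% | 79.2% | 79.0% |
| 0.2 | 4.7% | 4.9% | 79.7% | 80.4% | 79.4% |
| 0.3 | 4.5% | 4.8% | 80.1% | 82.1% | 78.8% |
| 0.5 | 3.7% | 5.0% | 83.0% | 89.0% | 78.9% |
| 0.7 | 2.7% | 5.1% | 87.0% | 97.0% | 79.0% |

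The Monte Carlo standard error near 5% is √(0.05 × 0.95/40,000) ≈ 0.1 point. Repeat runs gave 4.5–4.8% at ρ 0.2–0.3 and 3.8% at ρ 0.5, which agrees.

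**Step 3. Why the error falls below 5%.** When the covariate is flagged it is adjusted for, and the test is sound. When it is not flagged, the arms are close on it, so the treatment estimate varies less than the unadjusted standard error assumes and the test rejects too rarely. At ρ = 0.5 the rejection rate among unflagged trials was 3.26%. Weighting the two cases gives 0.279 × 5% + 0.721 × 3.26% ≈ 3.7%, which matches the table.

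**The case against.** The strongest reply is that the figures rest on a rule the protocol does not contain. No section makes an SMD of 0.20 an entry criterion, Section 9.4.5 is about baseline description, and comparability is one of two guides beside clinical relevance. That stands. A reader might infer that imbalance alone decides the models, but the text supports only that it influences them. Steps 1 and 2 show what would follow if the protocol's one measure were applied mechanically.

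Four further inferences are tempting and are not supported.

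- **That all models are affected.** The primary ANCOVA and the 18-month remission model have named covariates. The opening of the adjustment sentence in 9.4.3 is broad enough to leave doubt about the 18-month model, but its own list is the more specific text.
- **That the 27% applies to age, sex and site.** Sex and site almost never flag under stratification, and all three are named as adjusted for regardless.
- **That the rule inflates false positives.** Under the mechanical rule the error is below 5%, and power is no worse than with the covariate left out.
- **That the loss is large in general.** A comparison without the baseline outcome in the model would show bigger losses (at an effect of 0.5 SD, power 0.88 against 0.81 at correlation 0.5, and 0.97 against 0.85 at 0.7). Section 9.4.3 always keeps the baseline outcome in, and that is the covariate most likely to be so strongly correlated.

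It can also be said that full covariate lists for these endpoints belong in the SAP, and that age, sex and site are given only as examples, so duration is not excluded. That weakens the point about duration. It does not answer the contradiction, because the protocol states a selection principle that an SAP following it would inherit. Section 6.3 assigns the analysis to people outside screening and delivery, which helps with discretion, but it does not say that they are blinded to arm.

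**Conclusion.** The point holds as an internal contradiction in Section 9.4.3 for the other secondary endpoints: the covariates cannot be both prespecified and selected in part by observed comparability. The omission of diabetes duration by name is a real gap in the same place.

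The numerical effect depends on two assumptions: that an SMD of 0.20 or more would be the working trigger, and the partial correlation of the extra covariate with the outcome beyond its baseline value. On those assumptions the effect is conservative. At a correlation of 0.2 to 0.3 it is about 1 to 2 points of power, with type I error about 4.5–4.8%. It is material only for a strongly prognostic covariate: at 0.5, type I error is about 3.7–3.8% and power 83% against 89% for a fixed list. The protocol gives no value that would show such a covariate exists.

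The room for choosing a model after seeing data by arm is a separate risk. It is not quantified here and could act in the inflating direction. Severity: minor to moderate.

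**What to change.** In Section 9.4.3, delete baseline comparability as a criterion for selecting covariates. Fix one covariate list per secondary model in advance: the baseline value of the outcome where one exists, plus the four stratification factors (centre, sex, age group, and diabetes duration below 5 or at least 5 years). Where a binary model may be too sparse for that list, fix the shorter list in advance as well. In Sections 9.4.1 and 9.4.5, state that SMDs are descriptive only and do not drive model choice.

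The cost is about two sentences of analysis wording. No new data are needed, because all of these factors are recorded at baseline.
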